## 13 ASSESSMENT OF SAFETY

### 13.1 Safety Parameters

Safety Assessments at every visit include physical examination, vital signs, adverse event reporting, and clinical laboratory parameters (performed at the local labs in each study site).

Acute tolerability of IMP during initial dosing will be assessed by spirometry before and after inhalation.

**COVID-19 specific consideration:** In case the planned on-site visit cannot be performed, the PI or the Sub-Investigator and/or an appropriately qualified site study team member must call the patient to assess any potential adverse events (AEs) and to confirm the patient's status and wellbeing (see also [Section 14.2.8](#)).

#### 13.1.1 Adverse Events (AEs)

##### ***13.1.1.1 Definitions***

###### **Adverse Event (AE)**

An AE is any untoward medical occurrence in a patient after administration of a pharmaceutical product and which does not necessarily have a causal relationship with this treatment. An AE can therefore be any unfavorable and unintended sign (including an abnormal laboratory finding), symptom, or disease temporally associated with the use of a medicinal (investigational) product, whether or not related to the medicinal (investigational) product (ICH Guidelines for Good Clinical Practice, E6(R2), 9 November 2016).

This includes worsening of a pre-existing condition or increase in frequency of a pre-existing condition. An adverse event is considered serious if it meets any of the serious criteria listed below. To ensure no confusion or misunderstanding of the difference between the terms “serious” and “severe”, which are not synonymous, the following clarification is provided:

The term “severe” is often used to describe the intensity (severity) of a specific event (as in mild, moderate, or severe myocardial infarction); the event itself, however, may be of relatively minor medical significance (such as severe headache). This is not the same as “serious”, which is based on patient/event outcome or action criteria usually associated with events that pose a threat to a patient’s life or functioning. Seriousness (not severity) serves a guide for defining regulatory reporting obligations.

The official definition also extends to AEs occurring during the off-treatment follow-up period.

Each patient will be closely observed and questioned for AEs throughout the clinical trial period with non-leading questions (e.g., how do you feel?). The patients will be instructed to report to the clinical trial staff immediately any symptoms and/or signs which occur between the scheduled observation times.

All AEs reported by the patient or observed by the Investigator or hospital personnel will be documented in the respective eCRF. The following information regarding each adverse event will be obtained: date and time of onset and resolution (duration), serious or non-serious (as defined below), severity, treatment required, outcome, relationship to certain medication, and if the AE caused withdrawal from the clinical trial.

In addition to the Investigator's own description of the AE, each AE event will be coded by data management according to the MedDRA code list. The verbatim term will be recorded in the eCRF.

Abnormal laboratory test results will be reported as AEs if they are indicative of a clinical condition that meets the criteria for an AE.

#### Adverse Drug Reaction (ADR)

Adverse drug reactions (ADRs) are all noxious and unintended responses to a medicinal product related to any dose that a causal relationship between the medicinal product and an adverse event is at least a reasonable possibility, i.e., the relationship cannot be ruled out. An unexpected ADR is any adverse reaction not identified in nature, frequency, or intensity in the current Investigator's Brochure.

#### Serious Adverse Event (SAE)

Each adverse event is to be classified by the Investigator as SERIOUS or NON-SERIOUS.

The International Conference on Harmonisation (ICH) of Technical Requirements for Registration of Pharmaceuticals for Human Use defines a serious adverse event as any adverse event occurring at any dose that results in any of the following outcomes:

- Death
- A life-threatening event (immediate risk of death at the time of the event)
- Inpatient hospitalization or prolongation of existing hospitalization
- A persistent or significant disability/incapacity
- A congenital anomaly/birth defect
- Other important medical event (Medical and scientific judgment should be exercised in deciding whether expedited reporting is appropriate in other situations, such as important medical events that may not be immediately life-threatening or result in death or hospitalization but may jeopardize the patient or may require intervention to prevent one of the other outcomes listed in the definition above. These should also usually be considered serious.)

#### ***13.1.1.2 Relationship to Clinical Trial Treatment Assignment***

All adverse events will be evaluated by the Investigator for potential relationship to the clinical trial treatment assignment (L-CsA plus SoC or SoC alone) in the following categories:

- **Unrelated:** An AE for which there is no evidence of any causal relationship with the clinical trial treatment assignment
- **Possible:** An AE that might be due to the use of the clinical trial treatment assignment. An alternative explanation, e.g., concomitant drug(s), concomitant disease(s), is inconclusive. The relationship in time is reasonable; therefore, the causal relationship cannot be excluded.
- **Definite:** An adverse event that follows a reasonable temporal sequence from administration of the clinical trial treatment assignment; that follows a known or expected response pattern to the suspected clinical trial treatment assignment.

#### ***13.1.1.3 Maximum Intensity***

All adverse events will be graded according to the following:

- **Mild:** Event requiring no special treatment and generally does not interfere with usual activities.
- **Moderate:** Event that impairs usual activities but may be ameliorated by simple therapeutic maneuvers.
- **Severe\*:** Event which impairs usual activities and requires intervention.

\* There is a distinction between a severe adverse event and a serious adverse event; a severe reaction is not a serious adverse event unless it meets one of the criteria for serious events (see [Section 13.1.1.1](#)).

#### ***13.1.1.4 Serious Adverse Event (SAE) Reporting***

Any serious adverse events occurring

- between the first clinical trial procedure after obtaining informed consent and within 4 weeks after the completion of the EoT visit, whether or not considered related to the clinical trial treatment assignment  
or
- at any time after completion of the last follow-up and coming to the attention of the Investigator, if it is judged as related to the patient's participation in the clinical trial

**must be reported to CCI IMMEDIATELY, but within 24 hours upon knowledge**, as follows:

- Document the event in the eCRF within 24 hours of discovery
- Submit the SAE report by Fax or e-mail to a list of predefined recipients.
- Follow-up the SAE until the outcome is determined, providing periodic updates in the eCRF
- Provide any additional information if requested

Contacts of PPD are as follows:

PPD		PPD	
		PPD	

#### ***13.1.1.4.1 Timelines for Suspected Unexpected Serious Adverse Reaction (SUSAR) reporting to Competent Authorities and IRBs/ECs***

All suspected unexpected serious adverse reactions (SUSARs) will be reported by the Sponsor to the Competent Authorities and to the IRBs/ECs concerned as soon as possible, but within a maximum of 15 days (fatal or life-threatening SUSARs within a maximum of 7 days) of first knowledge.

Relevant follow-up information of fatal or life-threatening SUSARs will be communicated subsequently within an additional eight days.

#### ***13.1.1.4.2 Other Events to be Treated as Serious Adverse Events***

##### Exposure to drug during pregnancy/lactation:

In principle, pregnancy and the lactation period are exclusion criteria. In the event of a pregnancy occurring during the course of the clinical trial, the patient must be withdrawn from all IMP treatment immediately and permanently. The Sponsor must be notified without delay and the patient followed during the entire course of the pregnancy and postpartum period. Prenatal and neonatal outcomes must be recorded even if they are completely normal and without AEs. The SAE reporting procedure should be followed, even though pregnancy is not considered an SAE. No “serious criterion” should be checked. The SAE report form is solely used to ensure expedited reporting.

If any clinical trial patient becomes pregnant during the clinical trial period, the Investigator must contact Zambon SpA as the Sponsor of the clinical trial or its designee to discuss the management of the patient.

#### ***13.1.1.4.3 Investigational Medicinal Product Overdosing***

An overdose is a deliberate or inadvertent administration of a treatment at a dose higher than specified in the protocol. For the purposes of this clinical trial, any dose of aerosolized IMP administered to a patient that exceeds the dose foreseen in the protocol by more than 50% over 4 weeks should be reported as an overdose.

---

The Investigator/Sponsor responsibilities in regard to reporting SAEs are in accordance with the US Food and Drug Administration and other Competent Authorities concerned.

#### ***13.1.1.4.4 Events not Regarded as Adverse Events/Serious Adverse Events***

The following events will be not regarded as AEs/SAEs:

- Pre-scheduled (before any trial-related activities commenced) hospitalizations/surgeries/interventions
- Trial endpoint-related worsening; this will be assessed in the endpoint analysis.

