#### 9.4.3 Administration of L-CsA

Patients randomized to L-CsA treatment will receive L-CsA inhalation therapy in addition to SoC as outlined below.

Prior use in clinical trial 12011.201 and clinical trial AI 001 created no evidence suggesting L-CsA was intolerable to patients. However, patients with BOS typically have inflamed airways which could increase the likelihood of bronchospasm. Thus, to minimize risk to patients randomized to L-CsA, patients will receive training on the use of the device and the first dose of L-CsA [CC1]. In

addition, during all subsequent scheduled visits the L-CsA inhalation will be self-administered by the patient and under the supervision of trained personnel.

Each patient will ideally receive two L-CsA administrations per day, [CC1] [CC1]. The inhalations are scheduled to be taken approximately [CC1] [CC1]. Instructions for administration should be followed as described in the Instructions For Use.

If patients develop dyspnea or signs of drug intolerance at any point during the course of the trial, the site investigator should take appropriate actions, immediately. If clinically indicated, L-CsA will be held and rechallenged and/or discontinued. Patients will be encouraged to complete all remaining study visits through the end of the trial.

Patients who demonstrate signs of acute infection or acute rejection should be evaluated by the treating physician and treated appropriately. L-CsA should be continued if tolerated during this period. If L-CsA is held, it should be tracked in the eCRFs. The reasons for discontinuation or dosage adjustments have to be documented accordingly with specification of the date and reason on the respective case report form.

For those patients on inhalation therapy, reasons for temporary interruption may include the following:

- Significant acute respiratory infection requiring antimicrobial therapy until a clinical response is documented
- Respiratory failure from any cause until the event has resolved
- Mechanical ventilation

- If a significant decline in FEV1 (CCI      ) should occur associated with breathlessness or other respiratory symptoms.

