#### 12.1.2 Progression of BOS

Due to the patchy distribution of affected areas in the pulmonary allograft, chronic rejection and BOS are not uniformly detectable by biopsy. This method has turned out to be too unspecific and harmful for routine diagnostic use. Therefore, non-invasive spirometry has been routinely

---

established using standardized airflow measurements which nowadays is used to determine FEV1 as a surrogate marker for the diagnosis of BOS, its classification and its control of progression.

Progression of BOS during the treatment period is defined as a decline of FEV1 of  $\geq 10\%$  or  $\geq 200$  mL from Baseline FEV1 and absolute decrease in FEV1/FVC of  $> 5\%$  that is confirmed by measurements that are taken with **CCl** spirometer at least 2 weeks apart OR worsening in BOS Severity grade OR Re-transplantation, OR Death from respiratory failure.

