#### **12.1.9 Hospitalizations**

Hospitalizations for any reason other than a scheduled procedure should be regarded as serious adverse event and should be recorded in the eCRFs with admission date, discharge date, reason for admission, and additional diagnoses. If a patient requires mechanical ventilation for any reason other than a planned surgical procedure, dates of mechanical ventilation, and reason for mechanical ventilation should be recorded separately. A Hospitalization Discharge Summary may be requested by the Medical Monitor and shared with the DMC and/or AC.

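### Endpoint-related worsening, left undefined, is exempt from AE/SAE reporting against the protocol's own AE and SAE rules, so serious BOS events can be missing from the SAP's adverse event tables

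*Protocol*

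**What the plan says.** Protocol 13.1.1.4.4 names two kinds of event that are not AEs or SAEs. One is bounded: admissions and interventions already scheduled before any trial activity began. The other is not: "Trial endpoint-related worsening; this will be assessed in the endpoint analysis".

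Four other rules in the protocol point the opposite way:

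- **AE definition (13.1.1.1):** "This includes worsening of a pre-existing condition or increase in frequency of a pre-existing condition". BOS is pre-existing in every enrolled patient.
- **SAE definition (13.1.1.1):** an AE is serious if it results in death or in "Inpatient hospitalization or prolongation of existing hospitalization", among other outcomes.
- **SAE reporting (13.1.1.4):** any SAE from the first trial procedure after consent to 4 weeks after the end-of-treatment visit goes in within 24 hours, "whether or not considered related to the clinical trial treatment assignment".
- **Hospitalizations (12.1.9):** "Hospitalizations for any reason other than a scheduled procedure should be regarded as serious adverse event and should be recorded in the eCRFs".

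The endpoints reach well beyond a spirometry reading. The primary endpoint is FEV1 change. BOS progression (12.1.2) is met by confirmed FEV1 decline with a fall in FEV1/FVC, by a worse BOS grade, by re-transplantation, or by "Death from respiratory failure".

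SAP 15.3 plans tables of TEAEs, serious TEAEs and TEAEs leading to death. It does not mention the exemption or say how exempted events are handled.

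**The concern.** The exemption turns on a phrase that each site must interpret for itself. Treating physicians know the arm (Protocol 9.3.1). Under SAP 8.5 the investigator also has the final say on whether an event is BOS progression, even where the blinded Adjudication Committee disagrees. Whether a worsening counts as endpoint-related, and so escapes AE reporting, is therefore an unblinded judgment.

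Three outputs depend on that judgment: the AE tables in SAP 15.3, the DMC's review of AE trends (Protocol 13.2), and the stream of SAE reports from which suspected unexpected reactions are identified (13.1.1.4.1). They matter here because Protocol 15.5 gives a sufficient body of safety data as the reason for the revised enrolment target, and because SAP 14 makes all analyses descriptive.

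**Working it through.** No sample size, power or event figure in the documents bears on this point, so there is nothing to reproduce. The check sets the rules side by side for five kinds of event.

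| Event | Under 13.1.1.1, 13.1.1.4 and 12.1.9 | Under 13.1.1.4.4, read literally | Other route by which it is recorded |
|---|---|---|---|
| Unscheduled admission for worsening BOS | SAE | Can be exempt | Hospitalization entries (12.1.9, 14.2.3); hospital, ICU and ventilation days (synopsis) |
| Re-transplantation | Serious through the admission | Can be exempt, as a progression event | Date, reason and withdrawal (12.1.4); disposition (SAP 10); FEV1 set to zero (SAP 14.1.1) |
| Death from respiratory failure | SAE | Can be exempt, as a progression event | Medical monitor, with cause (12.1.5); BOS-related mortality (synopsis); FEV1 set to zero (SAP 14.1.1) |
| Symptomatic FEV1 decline after Visit 1, no admission | AE | Can be exempt | FEV1 by visit; FEV1 in the DMC review (13.2, SAP 8.4) |
| Asymptomatic FEV1 or BOS-grade change | Arguably an AE | Exempt | FEV1 by visit |

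**Can one rule be read as giving way to the other?** There are two candidates.

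1. *The exemption overrides.* It sits under the SAE reporting section, so it could be read as an exception to it. That still leaves 12.1.9, in a different chapter, which covers every reason for admission except a scheduled procedure.
2. *The specific rules override.* Then 12.1.9 settles BOS admissions. It does not settle a death outside hospital or a symptomatic decline without admission. Nor does the protocol say whether a re-transplantation admission counts as a scheduled procedure. Moreover, the SAE definition applies to an AE that leads to a serious outcome. If the worsening is declared not to be an AE, the outcome has no AE to attach to.

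Neither reading resolves all of the first four rows, and the protocol gives no order of precedence.

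**How sensitive are the tables?** SAP 8.2 reports 62 randomized. Assuming an even split, 62 / 2 = 31 per arm, so one patient left out of a row moves that arm's percentage by 1 / 31 = 3.2 points. This shows only how coarse the tables are. It does not estimate how many patients are affected.

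**Which way would omission act?** If L-CsA slows progression, more events are exempted in the SoC arm. If L-CsA lowers FEV1, the exemption hides events in the L-CsA arm. The documents do not fix the sign.

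**The case against.** The strongest reply is that a workable reading exists: the spirometric decline goes to the endpoint analysis and its serious consequences are still reported. The exemption speaks of worsening and names neither death nor hospitalization. Section 12.1.9 is explicit about admissions. The SAP appears to treat death as part of AE reporting, since SAP 9.2.3 describes an End of Study reason that groups death with adverse events, and SAP 15.3 plans a table of TEAEs leading to death. This has force. That deaths and admissions are covered is an inference from an undefined term together with 12.1.2. But the workable reading is not written down, and the literal one is available to every site.

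Three stronger readings might be inferred, and the documents do not support them:

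- **That these events disappear from the safety data.** They do not. The last column of the table shows another record for each. What can be lost is the AE/SAE report and the corresponding line in the SAP 15.3 tables. The other records do not restore either.
- **That acute drug-induced bronchospasm is hidden.** Protocol 9.4.3 does warn that "patients with BOS typically have inflamed airways which could increase the likelihood of bronchospasm", but it also says earlier trials gave no evidence of intolerability. Spirometry before and after the first dose, with cough and dyspnea recorded as AEs, covers initial dosing (Protocol 13.1.2, SAP 15.4). FEV1-based progression needs confirmation at least 2 weeks apart, which an acute episode would not ordinarily meet. The gap is symptomatic decline after Visit 1.
- **That mortality in the earlier investigator-initiated study measures the problem.** Those deaths accrued over five years, against 48 weeks here, and Protocol 7.1.4 gives no causes. Protocol 15.2.3.1 expects death, re-transplantation and consent withdrawal to be rare in this population.

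It is also fair to say that nothing shows investigators applying the exemption differently by arm. Parts of the endpoint lists and efficacy sections are redacted, so the full set of endpoint events cannot be seen. The redaction is not counted as a fault.

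**Conclusion.** The concern holds in a limited form. Protocol 13.1.1.4.4 sets an open-ended exemption that conflicts with 12.1.9, 13.1.1.1 and 13.1.1.4. As a result, BOS-related admissions, re-transplantations, respiratory-failure deaths and symptomatic FEV1 declines after Visit 1 can be left out of AE/SAE reporting and the SAP 15.3 tables, at the judgment of unblinded investigators. The conflict itself is plain on the page. Its consequence assumes that at least some sites apply the exemption literally, which the documents neither show nor rule out. The number of events affected and the direction of any imbalance between arms cannot be estimated.

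**What to change.** 1. **Protocol.** Reconcile 13.1.1.4.4 with 12.1.9, 13.1.1.1 and 13.1.1.4. Limit the exemption to a spirometric FEV1 or BOS-grade change without symptoms. State that deaths, re-transplantations, unscheduled hospitalizations and symptomatic declines remain reportable.
2. **SAP 15.3.** Enrolment is complete, so a clarification to sites may change little going forward. Add a by-arm table on the SAF of deaths, re-transplantations and unscheduled hospitalizations, drawn from all eCRF sources (AE, hospitalization and End of Study records). Reconcile it against the TEAE and serious-TEAE tables, and list any event found in one source but not the other.

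The cost is one clarification to sites, one extra table built from data already collected, some overlap with the SAP 10 disposition tables, and some AE entries that duplicate endpoint events.

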#### ***13.1.1.4.5 Duration of Follow-up after Adverse Events***

[figure not shown]
All adverse events should be followed until they are resolved or until a stable clinical endpoint is reached. The occurrence of AEs and SAEs will be monitored until 4 weeks after the EoT visit. Any patient with ongoing SAEs will be followed until recovery or stabilization of the SAE.

**COVID-19 specific considerations:** All confirmed cases of COVID-19, occurring after the patient has provided informed consent and until 4 weeks after the EoT visit, must be reported as SAE, and reported to **CCI** within 24 hours upon knowledge.

The seriousness criterion for COVID-19 hospitalized patients should be “hospitalization”; if the patient was not admitted to a hospital or the event is not resulting in prolonged hospitalization, the seriousness criterion “medically significant” should be used.

In all cases, details of the patient's symptoms, treatment and any clinically relevant information, should be entered in the SAE forms, as appropriate.

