### **13.2 Data Monitoring Committee (DMC)**

An independent Data Monitoring Committee (DMC) will be established to monitor the safety of IMP throughout the studies BT – L-CsA – 301 – SLT and BT – L-CsA – 302 – DLT. The DMC will monitor safety by evaluating the safety analysis generated by the unblinded independent statistician during the course of the clinical trial. Details of the safety analyses will be included in the DMC's Charter.

The DMC will evaluate treatment groups for possible trends in adverse events, determine whether the basic clinical trial assumptions remain valid, evaluate whether the overall integrity, scientific merit and conduct of the clinical trial remain acceptable, and make recommendations to the Sponsor.

The DMC will perform a comparison between the rate of observed COVID-19 cases, rate of patients withdrawal, and rate of missing data among trial participants in both treatment arms.

Members of the DMC will be unblinded to the treatment group label, i.e., the DMC will know which group is L-CsA + Standard of Care and which group is Standard of Care alone. The DMC will evaluate all safety and acute tolerability parameters, to be detailed in the DMC charter.

Safety and acute tolerability parameters include adverse events, acute tolerability of L-CsA, acute infections, malignancies, clinical laboratory data (white blood cell count with differential, red blood cell count, platelet count, alkaline phosphatase, alanine aminotransferase, aspartate aminotransferase, gamma glutamyl transferase, blood urea nitrogen, serum bilirubin, serum creatinine), vital signs, physical examinations and FEV1. The statistics provided will be merely descriptive.

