10 DISPOSITION

The number of patients screened, failed screening (patients who did not meet all eligibility criteria and was not randomized), enrolled (patients with informed consent and all eligibility criteria met or randomized), treated but not randomized, randomized (treated, and not treated with clinical trial treatment), completing clinical trial treatment (and reasons for not completing), and completing the clinical trial (and reason for not completing) will be presented in frequency tables by treatment group.

The number of patients in each analysis population (SAF, FAS, and PPS) will be summarized by treatment group. A by-patient listing of disposition will be provided.

All major protocol deviations will be presented as a frequency table by treatment group and in a by-patient listing for all randomized patients, which will include the category of the deviation, the deviation text, and whether the patient was excluded from PPS.

In addition, the counts on major COVID-19 related PDs will be provided, together with a by-patient listing for all COVID-19 related PDs.

In addition, a listing of the patients affected by Coronavirus Disease of 2019 (COVID-19) and their COVID-19 AE details will be provided for the FAS.

A table for the summary of stratification factors by treatment group for FAS and a separate listing of patients with mis-stratifications will be displayed.

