15 SAFETY DATA

15.1 General Considerations

Summaries of safety data (e.g., AEs, laboratory data, vital signs) will be provided for the SAF. No inferential analyses are planned for safety endpoints.

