15.3 Adverse Events

All AEs occurring during the clinical trial, whether or not attributable to study treatment, will be documented in the eCRF. All AEs will be coded to SOCs and PTs using the MedDRA dictionary (version 23.1).

Treatment-emergent adverse events (TEAEs) are defined as AEs with onset on or after the date of randomization.

The Investigator will assess the relationship (unrelated, possible, definite) of each AE to the clinical trial treatment assignment (L-CsA plus SoC or SoC alone). Treatment-related AEs are defined as events the Investigator considers to be possibly or definitely related to clinical trial treatment assignment.

All AEs reported in the eCRF will be presented in by-patient listings for the SAF.

The following summaries will be presented for AEs by treatment group and overall:

- Overview table including the number and percent of patients with
 - AEs;
 - TEAEs;
 - TEAEs leading to discontinuation of study treatment;
 - TEAEs leading study discontinuation;
 - TEAEs leading to death;
 - TEAEs by severity (Mild, Moderate, Severe);
 - Study treatment related TEAEs;
 - Serious TEAEs;
 - Serious study treatment related TEAE;
- TEAEs, grouped within SOC by decreasing frequency of PT;
- TEAEs by decreasing frequency of PT;
- TEAEs leading to discontinuation of study treatment, grouped within SOC by decreasing frequency of PT;
- TEAEs leading to study discontinuation, grouped within SOC by decreasing frequency of PT;
- TEAEs leading to death, grouped within SOC by decreasing frequency of PT;
- TEAEs by maximum severity, grouped within SOC by decreasing frequency of PT;
- TEAEs by relationship, grouped within SOC by decreasing frequency of PT;
- Serious TEAEs, grouped within SOC by decreasing frequency of PT;
- Related serious TEAEs, grouped within SOC by decreasing frequency of PT.

Patients who have multiple events coded to the same PT or within the same SOC will be counted only once in the patient counts for the corresponding summaries, but all events will be considered and listed. Table presentations will contain counts of patients, percentages of patients, and the number of events.

Any AE with missing relationship will be assumed related and summarized in the possible related category to clinical trial treatment assignment. Patients who experience the same event multiple times will be included in the most related category for summarization.

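### SAP 15.3 should also count patients with a serious event other than a COVID-19 case that is serious only by protocol rule, because the single serious TEAE count mixes the two and can distort the comparison between arms

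*Protocol*

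**What the plan says.** Under Protocol 13.1.1.4.5, every confirmed COVID-19 case "occurring after the patient has provided informed consent and until 4 weeks after the EoT visit, must be reported as SAE". A hospitalised case takes hospitalisation as its seriousness criterion. Otherwise, "if the patient was not admitted to a hospital or the event is not resulting in prolonged hospitalization, the seriousness criterion" is set to medically significant, with no severity threshold. The general SAE definition in Protocol 13.1.1.1 treats important medical events differently: "Medical and scientific judgment should be exercised in deciding whether expedited reporting is appropriate in other situations".

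SAP 15.3 plans an overview row with the number and percent of patients with serious TEAEs, a table of "Serious TEAEs, grouped within SOC by decreasing frequency of PT", and matching summaries of related serious TEAEs. None of these leaves COVID-19 out or splits events by seriousness criterion. Only post-randomisation cases enter: "Treatment-emergent adverse events (TEAEs) are defined as AEs with onset on or after the date of randomization".

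COVID-19 can be seen elsewhere:

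- SAP 10: "a listing of the patients affected by Coronavirus Disease of 2019 (COVID-19) and their COVID-19 AE details will be provided for the FAS".
- Protocol 13.2, repeated in substance in SAP 8.4: "The DMC will perform a comparison between the rate of observed COVID-19 cases, rate of patients withdrawal, and rate of missing data" by arm.
- SAP 15.3: tables carry numbers of events as well as patients, and a by-patient listing of serious TEAEs is planned.

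SAP 15.1 states: "No inferential analyses are planned for safety endpoints".

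**The concern.** The number of patients per arm with at least one serious event is the figure most readers will use to judge serious risk. Here it combines two kinds of patient: those with an event judged serious on its own merits, and those whose only serious event is a COVID-19 infection classified by a blanket rule. If the second group is sizeable, the comparison between arms reflects the rule as well as the treatment.

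This matters more than usual in this programme. The enrolment target of about 220 patients across BOSTON-1 and BOSTON-2 was set to obtain an adequately sized safety database (Protocol 15.5), and this trial's data feed it. SAP 14.2.5 accepts that the pandemic may have affected results, including through infections, and plans several COVID-19 analyses of FEV1. It plans no counterpart for serious events.

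**Working it through.** The plan states no serious-event rate, COVID-19 rate or precision target for safety, so it has no figure of its own to reproduce on this point.

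**Inputs.** From the documents: 62 patients randomised here (SAP 8.2) at 1:1 (Protocol 9.3), so about 31 per arm. Assumed: p, the proportion of patients with any other serious TEAE, 30% on SoC and 45% on L-CsA; c, the proportion with a COVID-19 case serious only by the rule, 10% to 40%; and independence of the two. Hospitalised COVID-19 belongs in p, because it is serious under the ordinary definition.

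**Step 1: c equal in both arms.** Observed proportion = 1 − (1 − p)(1 − c). The observed difference is therefore (p1 − p0)(1 − c).

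| c | SoC | L-CsA | Difference (points) | Ratio |
|---|---|---|---|---|
| 0% | 30.0% | 45.0% | 15.0 | 1.50 |
| 10% | 37.0% | 50.5% | 13.5 | 1.36 |
| 20% | 44.0% | 56.0% | 12.0 | 1.27 |
| 30% | 51.0% | 61.5% | 10.5 | 1.21 |
| 40% | 58.0% | 67.0% | 9.0 | 1.16 |

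For c = 20%: 1 − 0.70 × 0.80 = 0.44 and 1 − 0.55 × 0.80 = 0.56. A table that leaves out the rule-only cases returns the first line.

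**Step 2: c unequal.** Observed difference = (1 − p0)(1 − c0) − (1 − p1)(1 − c1).

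- c = 20% on SoC, 30% on L-CsA: 0.70 × 0.80 − 0.55 × 0.70 = 0.560 − 0.385 = 17.5 points, wider than 15.0.
- c = 30% on SoC, 20% on L-CsA: 0.70 × 0.70 − 0.55 × 0.80 = 0.490 − 0.440 = 5.0 points.
- Break-even at c0 = 20%: 0.560 − 0.55(1 − c1) = 0.15 gives c1 of about 25.5%. Above that, the gap widens.
- No true difference (p = 35% in both arms), c = 20% and 30%: 0.65 × 0.10 = 6.5 points of apparent excess.

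**Step 3: can the missing count be worked out from the tables?** Suppose 14 of 31 (SoC) and 18 of 31 (L-CsA) have any serious TEAE, and 9 per arm appear on the COVID-19 row (assumed counts). Because a patient is counted once, those with another serious event number between 14 − 9 = 5 and 14 on SoC, and between 18 − 9 = 9 and 18 on L-CsA. With equal denominators, the ratio lies anywhere from 9/14 = 0.64 to 18/5 = 3.6. Other preferred-term rows may narrow this range but do not settle it.

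**Step 4: event counts.** Adding the same event rate to both arms leaves the difference unchanged and moves only the ratio. For example, 0.6 and 0.9 per patient-year plus 0.2 each gives 0.8 and 1.1: the difference stays 0.3 and the ratio goes from 1.50 to 1.38. The distortion of the difference in Step 1 is therefore specific to the patient count.

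**The case against.** The strongest reply is that little is hidden and nothing turns on it. COVID-19 has its own preferred-term row. Because event numbers are tabulated, the COVID-19 row can be subtracted to give other serious events by arm. The planned listing of serious TEAEs shows treatment group, preferred term and severity, and with 62 patients those with a serious event other than COVID-19 can be counted by hand. The DMC compares COVID-19 rates. Deaths, discontinuations and maximum severity are tabulated without reference to the rule. No safety inference is planned, and Protocol 15 says analyses are not limited to those described, so a row can be added later.

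Much of this stands, and it lowers the priority. It does not close the gap. Subtracting the COVID-19 row removes hospitalised cases along with rule-only ones and yields events, not patients. The listing's stated minimum fields include seriousness but not its criterion. A hand count from a listing is not a planned result by arm, and a row added after the data are seen carries less weight than one fixed beforehand.

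A reader might also infer three stronger things that the documents do not support:

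- **That the rule pulls the arms' serious-event rates together.** This needs rule-only cases to be about equally common in both arms. In an open-label trial of an added inhaled immunosuppressant, incidence or detection could differ, and Step 2 shows movement either way.
- **That this trial was kept open for its safety data.** The target covers both trials, and this one was cut from 110 planned to about 50-60.
- **That the reporting rule is an error.** Other important medical events are part of the SAE definition, and applying that criterion to COVID-19 in immunosuppressed transplant recipients is a defensible conservative choice. The gap is in the tabulation.

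**Conclusion.** The point holds in a limited form. Every confirmed COVID-19 case is an SAE by rule, the SAP folds these into one patient count of serious TEAEs, and no planned table gives patients by arm with a serious event other than a rule-only COVID-19 case.

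If rule-only cases are equally common in the arms and independent of other serious events, the risk difference shrinks by 1 − c: from 15.0 to 12.0 points at an assumed c of 20%, and to 9.0 at 40%. If they differ by arm, the direction cannot be predicted. All rates are assumptions; the actual effect may be trivial or material. The harm is to the reading of a descriptive table, not to a planned test. Priority: minor to moderate.

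**What to change.** Leave the reporting rule and the existing serious TEAE total as they are. In SAP 15.3, before database lock:

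1. Add to the overview the number and percent of patients per arm with a serious TEAE, excluding COVID-19 events whose only seriousness criterion is medically significant under the protocol rule.
2. Repeat the serious TEAE table by SOC and PT with the same exclusion.
3. Show the excluded COVID-19 events by arm on a row of their own.

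Protocol 13.1.1.4.5 already requires the criterion to be assigned. If it is not in the analysis data, a flag from blinded medical review, as SAP 15.3.2 plans for malignancies, would serve.

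One limit should be footnoted: some excluded cases might have been judged medically important without the rule, so the two counts should be read together as a range. The cost is the added rows and one repeated table, from information already collected.
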